Specific Aim 2) To determine the impact of IR and inflammation on reward circuits and negative symptoms in patients with schizophrenia, before and after glucose challenge. Participants described in Aim 1 will undergo the following assessments before and after OGTT: 1) Resting-state and task-based fMRI to assess changes in activation of functional connectivity between the ventral striatum and other reward relevant brain regions using targeted and network-based analyses in relation to inflammatory and metabolic markers. 2) clinical and objective assessments of motivation and negative symptoms. Inflammatory versus metabolic responses to OGTT will be examined as predictors and controlled for in the analyses. *Hypothesis 2a:* Peripheral IR will be associated with decreased functional connectivity within reward circuits, decreased ventral striatum activation, and greater motivational deficits/negative symptoms post-OGTT. *Hypothesis 2b:* Inflammation will mediate the effects of IR on reward circuit functional connectivity, as well as changes in motivational deficits/negative symptoms before and after OGTT.

Study design and methods: Participants from Part A will be approached to enroll in this optional study. A new written informed consent will be obtained from all patients before protocol-specified procedures are conducted. The schedule of assessments for the optional OGTT study can be found in Table 5.

Figure 5: Part C OGTT Schedule of Assessments

Procedures	Screening Visit (Grady BHC)*	Visit 1 Pre-OGTT (Emory GCRC/FERN)	Visit 1 Post-OGTT (Emory GCRC/FERN)
Medical Assessments			
Physical Exam	X*		
Concomitant Medications	X	X	X
Adverse Events	X	X	X
Safety Labs**	X	X	
Vital Signs including waist circumference	X	X	X
CRP	X		
Additional Research Blood (immune and metabolic markers)		X	X
MRI Scan		X***	X
Neuropsychiatric Assessments			
Positive and Negative Symptom Scale (PANSS)	X^		
Brief Negative Symptom Scale (BNSS)	X^		
Calgary Depression Scale for Schizophrenia (CDSS)	X^		
Effort-Expenditure for Reward Task (EEfRT)		X	X
Neurocognitive Battery		X	X
Self-Reports/Questionnaires			
Profile of Mood States (POMS)		X	X

*If >6 months

**Safety labs may include complete blood count, urinalysis, urine drug screen, chemistry

***If Part C is completed within 2 weeks of Visit 2 from Part A of the protocol (or at the discretion of the PI), MRI data may be used from part A as pre-OGTT scan and the pre-OGTT MRI may be omitted.

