Power Analysis: For all three specific aims, analyses will be performed on data collected from 100 patients. Given that the primary statistical analyses will be correlational in nature, an N of 100 will be sufficiently powered (>80%) for moderate effect size ($r=0.5$) at an alpha = 0.05, two-tailed.¹¹⁶ All analyses will correlate inflammatory markers with both neuroimaging and behavioral task performance.

For the optional OGTT, to investigate the correlational relationships between inflammatory markers and metabolic markers, a sample size of 19 would be required to find a correlation of 0.7 at an alpha of 0.05 with Power of 0.95 (calculated in G*Power), which suggests that we have adequate power to investigate these primary relationships both before and after OGTT challenge. However, we are underpowered to identify relationships between changes in inflammatory and metabolic markers pre- and post-OGTT with reward circuitry or motivational deficits. These analyses are thus exploratory and will serve as preliminary data for future research proposals.

Interim Monitoring and Early Stopping:

Subjects will receive a physical examination at Part A Screening or Visit 1. Subjects will also receive safety laboratory testing as well as pregnancy (if female) and substance abuse testing at the Part A Screening or Visit 1, in addition to at Part A Visit 2.

The following events are considered sufficient reasons for discontinuing a subject from the study:

- An adverse event (AE) that, in the judgment of the investigator, may cause severe or permanent harm
- A clinical finding, such as an untreated medical condition, from safety labs or the history and physical examination
- Subject withdraws consent

- Subject lost to follow-up
- Pregnancy
- Protocol violation
- Substance abuse
- Death

Study:

If more than two individuals experience a reportable serious adverse event related to study procedures within a six-month period, the study will be stopped and reviewed by the DSMB.

Analysis Plan and Statistical Methods:

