Objective 2: Descriptive statistics will be used to characterize the mean, standard deviation, and standard error for each of these clinical and behavioral measures. For the EEfRT, proportion of hard-task choices across each level of probability as well as the difference between the proportions of hard task choices in low and high reward probabilities (effort allocation) will be calculated. Lower proportions of hard task choices indicate decreased motivation for monetary rewards. A larger difference in the proportion of hard task choices reflects more effort allocation. Regression analyses will be conducted to examine the relationship between task performance and concentrations of inflammatory markers (beginning with CRP). Regression analyses examining the relationship between changes in functional connectivity (Z scores) obtained using fMRI and changes in behavior and neuropsychological performance will also be conducted. In cases where data are not normally distributed, we will use standard transformation procedures to achieve normality, and/or use non-parametric tests of significance. The same covariates and data reduction strategies described above will be used in these analyses.

Objective 3: Formal mediation analysis will be conducted to assess whether functional connectivity mediates

the relationship between inflammation (as measured by inflammatory marker concentrations – beginning with CRP) and behavior (clinical ratings and objective measures, as described above). Bootstrapping will be used to provide an empirical estimate of the sampling distribution for indirect effects and will be used to generate confidence intervals for the purpose of inferential testing. A model of moderated-mediation will also be tested to assess whether mediation pathways are influenced by the presence of high vs. low baseline inflammation. Path analysis will be implemented using macros developed by Preacher and Hayes (<http://quantpsy.org/medn.htm>), which enable inclusion of covariates as well as possible moderators.

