Optional Study C Aim 1: Relationships between inflammatory and metabolic markers will be examined by linear regression at baseline and pre and post-OGTT. Change in these markers pre and post-OGTT will also be calculated and compared. Cytokines and their soluble receptors, as well as glucose-related markers at baseline, will be combined into a composite score based on the sum of Z-scores for initial analyses, then assessed individually by linear regression models with selection including clinical covariates. Covariates such as sex, age, race and BMI will be explored as potential confounders or mediators in all analyses.

Optional Study C Aim 2: Targeted FC for each subject and condition will be calculated as the degree of correlation in activity between 3mm³ radius spheres placed in four regions of striatum,^{57, 163 142}) that subserve reward processing and other goal-directed behaviors such as motor control,^{117,164} and the vmPFC ROI identified as being reward-sensitive in neuroimaging meta-analyses and as used to define vmPFC in our previous work (MNI coordinates x=0, y=44, z=-8, cluster size=1408 mm³ and encompassing parts of BA11 and ventral BA32 of ACC).^{57,163,165} Z-scores will be extracted for FC values at baseline and pre and post-OGTT. FC will be assessed between bilateral striatal seeds and the vmPFC ROI separately based on our previous work in MDD and IFN- α -induced depression,^{51,57} indicating that effects of inflammation are more pronounced on the left side. Linear regression models will be used to independently examine relationships between inflammation or metabolic dysfunction (Part C, Aim 1) and reward motor pathways. In our previously published work and Preliminary Data, use of inflammatory or metabolic measures as continuous rather than categorical variables were more sensitive for detecting associations with corticostriatal connectivity,⁵⁷ and will be the primary method for assessing relationships between inflammation or metabolism (as independent variables) and motivation and motor pathways (as dependent variables, including FC and behaviors). Covariates such as sex, age, race and BMI will be explored as potential confounders or mediators of relationships between biomarkers, brain and behavior.

8. Adverse Event Reporting

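### Part C Hypothesis 2b states a mediation path, but section 7 gives separate regressions and no indirect-effect model, and this is not reconciled with the adjustment described under Part C Specific Aim 2

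*Combined protocol and SAP*

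**What the plan says.** **The hypothesis.** Hypothesis 2b, under Part C Specific Aim 2, reads as follows: "Inflammation will mediate the effects of IR on reward circuit functional connectivity, as well as changes in motivational deficits/negative symptoms before and after OGTT". The exposure is insulin resistance and the mediator is inflammation. This point concerns connectivity as the outcome.

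**Adjustment described with the aim.** The same aim states: "Inflammatory versus metabolic responses to OGTT will be examined as predictors and controlled for in the analyses". No model is given there.

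**The analysis.** Section 7, Optional Study C Aim 2: "Linear regression models will be used to independently examine relationships between inflammation or metabolic dysfunction (Part C, Aim 1) and reward motor pathways". The sentence after it again joins inflammation and metabolism with 'or' when listing the independent variables. The only mention of mediators is: "Covariates such as sex, age, race and BMI will be explored as potential confounders or mediators of relationships between biomarkers, brain and behavior". Inflammation is not among those named.

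**What else section 7 offers.**
- Optional Study C Aim 1 covers the link between the two sets of markers: "Relationships between inflammatory and metabolic markers will be examined by linear regression at baseline and pre and post-OGTT".
- Objective 3 has a formal mediation analysis with bootstrap intervals. There connectivity is the mediator of "the relationship between inflammation (as measured by inflammatory marker concentrations – beginning with CRP) and behavior (clinical ratings and objective measures, as described above".
- The Power Analysis calls Part C underpowered to relate marker changes to reward circuitry or motivation, and treats those analyses as exploratory preliminary data.

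**The concern.** Mediation has two legs: exposure to mediator, and mediator to outcome with the exposure held fixed. The marker regressions of Part C Aim 1 supply the first. Nothing in section 7 supplies the second, or an estimate and interval for the product of the two.

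An analyst who follows section 7 literally would regress connectivity on inflammation, then on metabolic markers, and compare. If the two sets of markers are correlated, each can appear related to connectivity when only one matters. The results are meant to support future proposals, so an inflammation finding that really reflects insulin resistance could be carried forward as evidence for 2b.

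**Working it through.** **1. The plan's own figure.** The Power Analysis says "a sample size of 19 would be required to find a correlation of 0.7", with alpha 0.05 and power 0.95; sidedness is not stated for Part C.
- Fisher z, two-sided: n = ((1.960 + 1.645) / atanh(0.7))² + 3 = (3.605 / 0.8673)² + 3 = 20.3, so 21. One-sided gives 18.
- Exact bivariate-normal test, two-sided: power 0.946 at n=19 and 0.956 at n=20.

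The stated 19 is thus reproduced to within one patient of the exact two-sided 20, and the planned n=20 is adequate for r=0.7. The figure covers only the marker-to-marker leg. No figure is given for 2b.

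**2. What an inflammation-only regression shows if inflammation has no effect of its own.** The correlation between inflammation and connectivity is then

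r(inflammation, connectivity) = r(markers) × r(IR, connectivity).

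The two-sided rejection rate at n=20, by Fisher z, is Φ(d − 1.96) + Φ(−d − 1.96), with d = atanh(|r|) × √17.

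The documents give no correlation between insulin resistance and connectivity, so the second column is assumed. The marker correlation of 0.7 is the value the sample size was set to detect, not an observed one, so lower values are shown as well.

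| Marker r | IR–connectivity r | Implied r | d | Significant |
|---|---|---|---|---|
| 0.3 | −0.5 | −0.15 | 0.62 | 10% |
| 0.7 | −0.3 | −0.21 | 0.88 | 14% |
| 0.5 | −0.5 | −0.25 | 1.05 | 18% |
| 0.7 | −0.5 | −0.35 | 1.51 | 33% |
| 0.7 | −0.6 | −0.42 | 1.85 | 45% |

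**3. Separate against joint model.** In simulations of 1,000 data sets at n=20, with marker correlation 0.7 and no inflammation effect, the inflammation-only regression was significant in 34% (insulin-resistance effect of size 0.5) and 63% (size 0.7). The inflammation coefficient in a model containing both was significant in 5% and 4%.

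**4. Price of the joint model.** At marker correlation 0.7 the variance inflation factor is 1 / (1 − 0.7²) = 1 / 0.51 = 1.96, so standard errors rise by √1.96 = 1.4. Simulated power of a percentile-bootstrap test of the indirect effect at n=20, with no direct effect, was:

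| IR to inflammation | Inflammation to connectivity | Power |
|---|---|---|
| 0.7 | 0.3 | 17% |
| 0.5 | 0.5 | 33% |
| 0.7 | 0.5 | 37% |
| 0.7 | 0.7 | 70% |

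These standardized paths are assumptions too.

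**The case against.** **Adjustment is stated.** A reader might infer from section 7 that the two effects will never be separated. The documents do not support that. Specific Aim 2 says both responses will be predictors and controlled for, and 'independently' could mean independent contributions rather than separate models. This stands. What remains is that the two places are not reconciled, that no joint model is written down, and that adjustment alone does not yield an indirect effect.

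**Part C's main question is elsewhere.** A reader might also infer that Part C cannot answer its central question. Its introduction sets out to test whether insulin resistance drives inflammation, and the Power Analysis treats the marker-to-marker correlations as primary. Aim 1 does analyse those. This stands, although the introduction also names the contributions of metabolic dysfunction and inflammation to reward circuitry as a purpose.

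**The analyses are already exploratory.** True for those relating marker changes to circuitry and motivation, and it limits the importance. It answers imprecision, not attribution: the association in step 2 does not go away in a larger sample.

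**The percentages are not false-positive rates.** This also stands. In those scenarios the marginal correlation is real, and rejecting it is correct as a statement of association. Nor do separate models nearly always misattribute: the illustrated rates run from 10% to 45%, and they depend on assumed inputs.

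**A mediation model would not settle direction.** The Part C introduction describes insulin resistance and inflammation as each acting on the other. A one-direction model at n=20 cannot establish causal order. This stands and shapes the fix.

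**Conclusion.** The point holds in limited form. Section 7 as written cannot test the connectivity part of Hypothesis 2b, because it specifies no joint model and no indirect effect, and the Objective 3 mediation has a different exposure, mediator and outcome. Section 7 also needs to be reconciled with Specific Aim 2.

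The gap itself rests on the text alone. Its size is illustrative. If inflammation has no effect given insulin resistance, an inflammation-only regression would be significant in about 10% to 45% of studies at n=20 for the tabulated inputs, against about 5% in a joint model. This misleads only if read as an effect of inflammation separate from insulin resistance.

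Severity is minor: an optional sub-study of 20 participants, with no bearing on the main Part A analyses.

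**What to change.** In section 7, Optional Study C Aim 2, add for Hypothesis 2b:
- one connectivity model with HOMA-IR and the inflammatory composite together, the composite being kept apart from the glucose-related markers;
- the indirect effect of HOMA-IR through inflammation, with a bootstrap interval, using the macro already cited for Objective 3;
- estimates and intervals reported as exploratory, in line with the Power Analysis;
- a statement that causal order is not established, given the two-way relation described in the Part C introduction.

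Align the sentence in Specific Aim 2 with this model. The alternative is to reword 2b as an association and keep the separate regressions.

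The cost is wording; no new data or software are needed. The downside is wide intervals at n=20 (variance inflation 1.96 if the markers correlate at 0.7), which fairly reflects what a sub-study of this size can show.
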